Body Composition and Adipose Tissue in HIV Lipodystrophy: Effects of Tesamorelin Therapy

NCT03226821

IRB approval date: Nov 10, 2021

BACKGROUND

Study Purpose and Rationale

HIV lipodystrophy is increasingly recognized as a common and clinically significant long-term sequelae of HIV treatment. In the HIV lipodystrophy lipohypertrophy phenotype, which we will study, VAT is increased and this is associated with reduced GH secretion (1, 2). Mounting evidence also links this phenotype with dyslipidemia, insulin resistance, subclinical atherosclerosis and CV disease in patients with HIV disease (3-8). The etiology of HIVLD with central adiposity is unclear, but this phenotype is increasingly common with newer, less lipotoxic combination anti-retroviral therapy (cART) use (9). VAT and hepatic lipid accumulation, are important health concerns for HIVLD patients (10-12).

GH modulates fat metabolism and is known to be lipolytic (13-15), especially in VAT (16-21). Other evidence also suggests that GH reduces hepatic fat content, which seems to track with VAT mass in other clinical settings. Rodent and GH deficiency (GHD) data suggest that reduced GH action in liver increases hepatic lipid. Mice with impaired GH signaling or receptor deletion have increased hepatic lipid and steatosis (22, 23) and in case reports hepatic lipid was increased in GHD patients (24-26). This is a clinically important, but under-recognized feature of GHD, which may progress to NASH. A few small studies found that GH therapy reduced VAT (27-29), but liver fat changes were inconclusive (29, 30). GH therapy effects on liver fat require further study.

This project will test our primary hypothesis that GH is a negative regulator of liver fat in HIVLD patients by testing for a reduction of liver fat with GHRH analogue treatment. A GHRH analogue (tesamorelin) stimulates GH secretion and reduces VAT in HIVLD patients (31, 32). Tesamorelin therapy stimulates pituitary GH secretion and restores the deficient GH secretion seen in HIVLD. This is demonstrated by a rise of IGF-1 levels, a marker of overall GH secretion, in patients with HIVLD. Tesamorelin therapy of HIVLD with central adiposity has been shown to reduce VAT (31, 32). However, studies to date used only single slice abdominal CT and DXA to assess body composition (32-34). Recently, in a 1H MRS study tesamorelin reduced liver fat (32). Our study adds to this work with its total body MRI assessments combined with direct examination of biopsied adipose tissue before and after tesamorelin. Whole-body scanning is advantageous and

more accurate than single-slice imaging (35-37). Our study will provide novel data on tesamorelin's effects on HIVLD and liver fat accumulation, both increasingly recognized as important long-term complications of HIV infection (10-12). Our findings will help elucidate GH's role in liver fat accumulation, a precursor to hepatic steatosis and NASH (38), a significant health problem in the general population.

The actions of GH in adipose tissue are central to its effects to reduce adipose tissue mass. GH may have effects both on adipocytes as well as inflammatory cells in adipose tissue. Thus GH effects in adipose tissue may importantly relate to adipose tissue and thus circulating inflammation in disorders of GH secretion. In our ongoing study examining the effects of GH excess on adipose tissue changes in acromegaly, our preliminary identified that GH produces a unique adipocyte-immune cell phenotype that contributes to circulating inflammation and insulin resistance and may alter adipose tissue energy metabolism. Our hypothesis stems from our identification in preliminary work of a novel and unexpected GH-induced dissociation of inflammatory & immune phenotypes. Specifically, we found a pro-inflammatory pattern of adipocyte activation yet suppression of macrophage inflammation that reverses with acromegaly treatment. GH-induced increased lipolysis may initiate these effects. GH increases HSL, reduces LPL activity and activates the α -adrenergic 3 receptor (18, 39-44). GH also inhibits lipogenesis and reduces AT mass (41, 45). In other models, disordered lipid metabolism promotes lipolysis and FFA release leading to pro-inflammatory cytokine release. This inflammatory response then promotes insulin resistance in adipose tissue (46-55). Thus, cytokines released by inflamed adipose tissue may play a role in GH induced insulin resistance. The effect of GH excess on AT inflammation had not been examined before our study. By contrast, in other models, activation of inflammatory (adipocyte cytokine) and immune (macrophage) components of AT parallel each other. Our findings are supported by recent in vitro data that GH induces pro-inflammatory cytokines in pre-adipocytes yet suppresses inflammatory cytokines in macrophages (56). This study examined isolated cells (56, 57), ours provides evidence of this effect in vivo. In this study, we will test the effect of restoration of GH secretion through administration of GHRH analogue therapy on AT inflammation in HIVLD groups. In patients with GHD with central obesity, as shown in a cross-sectional study, SAT phenotype may be similar to that of general obesity, namely increased adipocyte size and expression of pro-inflammatory factors and macrophage infiltration (58).

Effects of GH therapy are unknown, but it may reduce both adipocyte and macrophage inflammation.

This study will determine the effects of GHRH analogue therapy on adipose tissue inflammation in HIVLD. In patients with GHD and central obesity, as shown in a cross-sectional study, SAT phenotype may be similar to that of general obesity, namely increased adipocyte size and expression of pro-inflammatory factors and macrophage infiltration (58). Effects of GH therapy are unknown, but it may reduce both adipocyte and macrophage inflammation. In the few studies that directly examined SAT in patients with the HIVLD and the central lipohypertrophy phenotype, induction of pro-inflammatory cytokines such as TNF, macrophage infiltration and impaired mitochondrial function were present in both abdominal SAT and VAT (59-61). However, VAT was hypertrophied, but central SAT may not be, possibly reflecting greater sensitivity of SAT to toxic inflammation(59, 62, 63). Our study is unique since the direct effects of tesamorelin on adipose tissue have not been studied. We will focus on how tesamorelin modulates the adipose tissue inflammatory/immune phenotype. Animal models suggest that GH sufficiency is needed to maintain an anti-inflammatory phenotype in adipose tissue (57, 64). Thus, restoration of GH action in adipose tissue in HIVLD may be important to reducing inflammation in adipose tissue and thus systemically and reducing these patients' long-term CV risk.

We will also test for new mechanisms by which GH supplementation with tesamorelin may alter lipid and energy metabolism in adipose tissue in HIVLD. Genes implicated to mediate these processes have never before been studied in paired adipose tissue samples from before and after GHRH analog treatment in HIVLD patients. Utilizing our unique tissue set, we will examine expression of genes for enzymes believed to mediate GH-induced reduction in adipose tissue lipid stores and others recently found altered by GH therapy including CIDEA (lipolysis and energy balance regulator) and PLPLA3 (lipid hydrolase) (41). We will examine expression of genes for fatty acid desaturases. These are linked to diabetes (65) and increased in GH transgenic mice (66) and acromegaly in a small cross sectional study (67). We will study the gene for PIK3R1 (p85), an enzyme important to insulin's metabolic actions and that was induced by GH in mouse adipose tissue (68), and the gene for TCF7L2, a transcription factor insulin resistance and upregulated in SAT in patients with insulin resistance(69) and acromegaly(67). We will explore the possible effect of HIVLD and its treatment with GHRH analog therapy on the transformation of white adipose

tissue (WAT) to the more energetically favorable brown adipose tissue (BAT). GH deficiency may have a negative impact on the WAT to BAT transition. Emerging evidence links immune cell phenotype, in particular that of macrophages with M2 characteristics, to regulation of WAT “browning” (70-72). With GHRH analog therapy, alternative M2 macrophage recruitment into adipose tissue may be associated with a relative “browning” of WAT. To test this hypothesis we will examine relative expression of genes associated with this process before and after GHRH treatment. These studies will provide valuable new insights into the mechanisms by which GH deficiency its therapy with tesamorelin disrupt adipose tissue health in HIVLD.

GH effects on circulating inflammatory cells in GH disorders may relate to their associated CV risk. Thus, we test our Hypothesis that the inflammatory profile of circulating monocytes mirrors that of adipose tissue macrophages (ATMs) before and after tesamorelin therapy. A significant portion of ATMs are derived from circulating monocytes(73). Thus, we hypothesize that GH’s anti-inflammatory effect on ATMs will be detectable in circulating monocytes. We will examine circulating monocytes for our adipocyte-immune cell pattern before and after tesamorelin treatment. GHD and HIVLD increase CV risk. In a prior study, GH therapy in patients with GH deficiency due to pituitary disease had reduced peripheral monocyte TNF and IL-6 expression (74), supporting our hypothesis that GH suppresses monocyte and macrophage inflammation. Since monocytes and macrophages play key roles in atherosclerosis development (75, 76), an activated, pro-inflammatory monocyte profile in HIVLD with central adiposity could lead to circulating inflammation and increase CV risk in these patients. GH supplementation with GHRH therapy could help reverse this pattern. These data may help elucidate the nature of the relationship between circulating immune cells and atherosclerosis in disorders of GH secretion or action.

Thus, the purpose of this project is to examine the effect of GHRH analog therapy (tesamorelin) on liver fat and central adiposity in patients with HIV lipodystrophy. This project also examines adipose tissue macrophage infiltration, pro-inflammatory cytokine, adipokine and macrophage activation marker gene expression as well as circulating adipokine and inflammatory cytokine levels before and after GHRH analog therapy.

With the collaboration and expertise of [name], this project will be the first to directly examine the effect of HIV lipodystrophy with central adiposity and its treatment with the GHRH analog tesamorelin on adipose tissue macrophage infiltration and inflammatory cytokine and

adipokine expression, which are now recognized to have a central role in insulin resistance, diabetes, vascular disease and fatty liver, all relevant to morbidities of HIV lipodystrophy.

Research Aims & Abstracts

The primary hypothesis to be tested is that therapy with the GHRH analog tesamorelin, which augments GH secretion), will reduce hepatic lipid and visceral adipose tissue mass in patients with HIV lipodystrophy and central adiposity. The second hypothesis to be tested is the tesamorelin therapy will reduce adipose tissue inflammation and circulating pro-inflammatory markers on macrophages in these patients.

STUDY DESIGN

The CORE study is an open-label, single arm prospective study of tesamorelin therapy of patients with HIV lipodystrophy.

Enrolled subjects will have a screening visit and 6 visits - a baseline visit before starting tesamorelin, a visit at 1 month, 3 months, 6 months, 9 months and at 1 year of tesamorelin (GHRH analogue) therapy. Blood sampling for safety labs and clinical examinations will be performed at each visit. At the baseline, 6 month and 1 year visits subjects will also undergo body composition testing by total body MRI/MRS, adipose tissue biopsy, indirect calorimetry, FSIGT and additional blood sampling. Tesamorelin is being used in this study as per its FDA approved indication and dosing for treatment of HIV lipodystrophy with central adiposity. Tesamorelin, 2 mg, will be taken daily by patients by subcutaneous self-injection

Subject Inclusion Criteria:

- HIV-infected subjects with HIV lipodystrophy (HIVLD) and abdominal fat accumulation.
- Males and females
- Ages 18-65 years
- Waist Circumference (WC): 102 cm for men, 88 cm for women (ethnicities except East/South Asians) 90 cm for men, 80 cm for women (East/South Asians)
- CD4 count >100 cells/mm³.
- HIV RNA load < 400 copies/mL

- Fasting glucose <150 mg/dL
 - Patients with mild diabetes (HbA1c<7%) that is well controlled with diet and/or oral diabetic agents besides TZDs are eligible.
- Stable antiretroviral therapy for 8 weeks (any regimen).

Exclusion criteria:

- Diabetes mellitus that is not well controlled
- History of malignancy

Study procedures

Patients who are interested in the study will first undergo screening. Screening which consist of a telephone interview to further explain the study and confirm the subjects' interest and eligibility and a review of medical records for the above entry inclusion and exclusion criteria. If needed to obtain information on entry criteria not available from the medical record, subjects will have a brief screening visit in person to obtain additional information. If subjects meet all entry criteria and agree they will be enrolled.

Enrolled subjects will have 6 visits - a baseline visit before starting tesamorelin, a visit at 1 month, 3 months, 6 months, 9 months and at 1 year of tesamorelin (GHRH analogue) therapy. Blood sampling for safety labs and clinical examinations will be performed at each visit. At the baseline, 6 month and 1 year visits subjects will also undergo body composition testing by total body MRI/MRS, adipose tissue biopsy, indirect calorimetry, FSIGT and additional blood sampling.

Study Drug Tesamorelin is being used in this study as per its FDA approved indication and dosing for treatment of HIV lipodystrophy with central adiposity. Tesamorelin, 2 mg, will be taken daily by patients by subcutaneous self-injection at rotating sites on the abdomen. Safety assessments including measurements of fasting blood glucose and liver function tests and clinical examinations for signs and symptoms of GH excess or local injection site reactions will be performed at 1 month and every 3 months of therapy.

At the baseline, 6 month and 1 year visits subjects will undergo body composition testing, adipose tissue biopsy, indirect calorimetry for measurement of REE (resting energy expenditure), FSIGT and fasting blood sampling.

Body composition testing: Anthropometrics and total body MRI and ¹H-MRS after a 12 hour fast.

Anthropometric measurements: Subjects will have measurements of waist circumference with a tape measure and height and body weight will be measured.

Total body MRI: Quantification of total and regional body composition by whole body multi-slice MRI, liver fat by Modified DIXON method (35, 79), and ¹H-MRS (magnetic resonance spectroscopy) assessment of intra-hepatic lipid (IHL) and IMCL of the anterior tibialis muscle will be performed at the Columbia Hatch MR Research Center as previously described (80, 81). Analyses will be done in the NY Obesity Research and Nutrition Center Image Analysis Lab on the CUMC campus and under the direction of [name] (80, 81). The analysis will include measurement of inter-muscular AT (IMAT)(AT between muscle groups and beneath the fascia (82, 83), which is distinct from intra-myocellular lipid (IMCL)(lipid in myocytes). MRIs will be analyzed by the same experienced reader blinded to study conditions using SliceOmatic software (TomoVision) (82, 84). Liver fat will also be determined by Modified DIXON method performed during the total body MRI sequences. It has advantages of not requiring ROI selection during acquisition and measures fat for the entire liver. DIXON is validated against MRS (35, 79).

Adipose tissue biopsy: After a 12-hour fast, subjects will undergo abdominal subcutaneous AT biopsy by the PI at the umbilicus level. Alternating sides of the abdomen will be samples on serial biopsies. After local anesthesia, 2-4g of AT will be using aspirated using a 15g needle. Pieces will be immediately frozen in liquid nitrogen & stored at -80°C, others are fixed for immunohistochemistry.

Indirect Calorimetry (TrueOne2400, ParvoMedics) will measure resting energy expenditure (REE) after an overnight fast (12hr.) and 30 min. of rest with subjects still, awake and supine in a thermoneutral environment. REE will be determined from the last 20 minutes of 30 minutes of gas exchange results (85). The cart is calibrated prior to each test (86).

Insulin-modified frequently sampled intravenous glucose tolerance test (FSIGT) with reduced sample number (n=12)(87) will be performed to assess insulin sensitivity. In this protocol, a 300 mg/kg bolus of glucose will be administered after an overnight fast followed by an infusion of 0.03 units/kg of insulin 20 minutes later. In the reduced sample model, 12 blood samples (insulin and glucose) will be drawn at times 0, 2, 4, 8, 19, 22, 30, 40, 50, 70, 90 and 180 minutes (22). The data will be analyzed by Bergman Minimal Model to calculate our outcome measures, insulin

sensitivity index (Si) and disposition index (DI) to estimate B-cell function (87-92). FSIGT is used extensively to assess insulin sensitivity and provides estimates that correlate well with those of the clamp in non-diabetics (87, 91, 93).

Blood Sampling: Fasting serum or plasma samples will also be obtained for IGF-1, GH, leptin, FFA, glucose, TNF, IL-6, hsCrp, adiponectin (high molecular weight & total), leptin and lipid panel.

Peripheral blood mononuclear cell collection: A sample (2 tbsp.) of heparinized blood will be obtained. Peripheral blood mononuclear cells will be isolated by density centrifugation using Ficoll (Life Technologies). Recovery of highly purified monocytes will be performed by flow cytometry with fluorophore conjugated anti-CD14 primary antibody. Cells will be analyzed on a FACSCalibur and analysis performed using CellQuest software (Becton Dickinson). Monocytes will be separated using a FACSaria cell sorter (BD Biosciences). CD14⁺ cells will be centrifuged and immediately frozen for later gene expression analysis. PCR will be performed in batches for gene expression of TNF, IL6, MCP-1, IL1-B, IL-4. A complete blood count will be performed from this sample.

The total amount of blood drawn at baseline, 6 month and 1 year visits will be 4 tablespoons and at the other visits it will be ½ tablespoon.

Blood sampling for safety labs and physical examinations: At each visit, blood will be drawn for liver function tests (AST, ALT), and fasting blood sugar. Subjects will also have a physical examination including measurement of vital signs, temperature and examination for signs and symptoms of GH excess such as edema and local skin reactions.

Adipose Tissue Analyses: Frozen and fixed adipose tissue samples will be later analyzed in batches.

Immuno-histochemical analysis: Macrophage antigen, CD68, expressing cells fraction/sample will be calculated to determine macrophage content (94). Adipocyte size will be measured (Image-Pro Plus, Media Cybernetics, Bethesda, MD) (95) and size distribution will be quantified (96). Adipocyte count, counts of crown-like structure and other immune (T, NK) cells and fibrosis analysis will be conducted (97). Sample processing and analyses will be uniform and paired samples will be directly compared. Quantitative RT PCR will be performed on total RNA extracted from frozen AT as described (94). Relative expression values will be determined for: adipocyte-specific genes adiponectin (ADIPOQ) and leptin (LEP), proinflammatory genes (TNF,

IL6), genes of macrophage activation markers (CD11c, CD68, MCP-1, IL1- Genes associated with AT “browning” (UCP-1, DIO2, CIDEA, PGC-1, PRDM-16), and lipid metabolism, (CIDEA, PLPLA3, SCD, PIK3R1, TCF7L2). We will use control genes to normalize data (94). Samples are analyzed in labs of [name] and NYONRC AT core.

HORMONE ASSAYS: Hormones and other markers will be measured with the following assays: IGF-1 (WHO 02/254) & GH (WHO 98/574, 22kDa GH specific antibody), IDS-iSYS chemiluminescence assay; IGF-1 & GH (WHO 98/574, 22kDa & 20kDa antibody), Insulin, IGFBP-3, hsCRP - chemiluminescent immunometric (Immulite, Siemens); HbA1C, glucose, lipids (Cobas Integra, Roche); Adiponectin (total & HMW)- ELISA (Millipore); Leptin- RIA (Millipore); FFA - enzymatic colorimetric (WAKO); IL-6 & TNF -ultrasensitive ELISA R & D.

STATISTICAL PROCEDURES

The primary outcome to be examined will be change in hepatic lipid content and the secondary outcome will be change in VAT mass with tesamorelin therapy. Additional outcomes examined will be changes in relative gene expression of adipose tissue genes, change in Si, REE and changes in other hormones and markers with tesamorelin therapy.

The general analytic approach will be to compare baseline to post-therapy parameters in each subject by paired t-test. Repeated measures ANOVA will test adipose tissue mass change over time. Correlations between variables will be tested by Pearson’s correlation. Non-normally distributed data will be log-transformed or nonparametrics used. Multiple comparisons corrections and post-hoc tests will be used. Macrophage content (% CD68 positive cell per sample) and average adipocyte cross-sectional area will be compared in HIV lipodystrophy patients adipose tissue before vs. after tesamorelin therapy by paired t-test. Adipocyte area and macrophage content will be correlated with BMI and fat mass. Correlations between gene expression data and body mass or AT mass will be compared by a nonparametric approach. Ratios of macrophage content or relative gene expression per kg AT will be compared in patients before & after treatment by appropriate t-tests. For analysis of the blood samples differences between baseline and final study visit for each marker will be compared by paired t-test. Patterns and time course of change in serum and adipose tissue inflammation will be descriptively compared. Matching serum/gene expression marker changes will be correlated.

Sample Size is based on the number of subjects needed to detect a significant decrease in hepatic lipid with tesamorelin therapy. Preliminary data from our acromegaly treatment study were used for this estimation. Sample size of 24 pairs has 88% power to detect a hepatic lipid change of 2% with a SD of 3% at $\alpha = .05$ and 12 pairs of each gender has 80% power to detect this hepatic lipid change within gender group with a within-gender SD of 2% at $\alpha = .05$ using a two-sided paired t-test.

REFERENCES

3. Stanley TL and Grinspoon SK (2012) Body composition and metabolic changes in HIV-infected patients. *The Journal of infectious diseases* 205 Suppl 3: S383-90. 3349298.

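### The entry criteria and procedures say nothing on pregnancy, and they admit patients with known pituitary disease to a year of a drug that works through the pituitary

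*Combined protocol and SAP*

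**What the plan says.** The inclusion list under STUDY DESIGN admits "Males and females" and "Ages 18-65 years". The exclusion list has two lines: "Diabetes mellitus that is not well controlled" and "History of malignancy".

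Under Study procedures, screening is a telephone interview plus "a review of medical records for the above entry inclusion and exclusion criteria". An in-person screening visit takes place only if the records leave an entry criterion open. The enrolment rule follows: "If subjects meet all entry criteria and agree they will be enrolled".

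Treatment is a daily self-injection, with "a visit at 1 month, 3 months, 6 months, 9 months and at 1 year of tesamorelin (GHRH analogue) therapy". FSIGT and an abdominal fat biopsy are done at baseline, 6 months and 1 year. Safety labs at each visit are AST, ALT and fasting glucose, with vital signs and an examination for signs of GH excess and skin reactions.

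On mechanism, Study Purpose and Rationale says: "Tesamorelin therapy stimulates pituitary GH secretion and restores the deficient GH secretion seen in HIVLD".

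Pregnancy, pregnancy testing, breastfeeding and contraception are mentioned nowhere. Pituitary disease as a diagnosis appears only in the background, in connection with an earlier study of GH therapy.

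**The concern.** Screening checks only the listed criteria, so a condition that is not listed is not looked for. Two omissions matter.

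The first is about safety. Women of child-bearing age are eligible, and the by-gender power calculation assumes 12 of them. Followed as written, the plan has no step that would find a pregnancy before the first dose, and nothing in its criteria would keep a woman known to be pregnant from enrolling.

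The second is about what the trial tests. The primary hypothesis is that raising GH lowers liver fat, and the drug raises GH through the pituitary. A patient whose pituitary responds poorly contributes a pair to the primary paired t-test but gives little or no information about that hypothesis. With a single arm, the result is the mean within-patient change, and each such patient pulls that mean towards zero.

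**Working it through.** **Would anything in the plan catch either group?**

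| Element of the plan | Pregnancy | Pituitary or hypothalamic disease |
|---|---|---|
| Two listed exclusions | Not covered | Not covered, unless the cause was a malignancy |
| Interview and record review | Tied to listed criteria, so not sought | Tied to listed criteria, so not sought |
| AST, ALT, fasting glucose | Would not detect it | Would not detect it |
| GH and IGF-1 sampling | Not relevant | Sampled as study markers, with no entry rule attached |
| Statement that use follows the approved indication and dosing | Adds no exclusion | Adds no exclusion |

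No row closes either gap.

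**How much could non-responders dilute the primary test?**

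Inputs from STATISTICAL PROCEDURES: 24 pairs, change of 2%, SD 3%, two-sided paired t-test at 0.05, stated power 88%. The number of patients with no response, k, is not in the documents. It is an assumption, shown here from 0 to 3.

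*Step 1: reproduce the plan's figure.* Power comes from the noncentral t distribution with n - 1 = 23 degrees of freedom and noncentrality change / (SD / √n) = 2 / (3 / √24) = 2 / 0.612 = 3.27. This gives 87.8%, which agrees with the stated 88%.

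*Step 2: dilute.* If k of 24 patients have zero response and the rest average 2%, the mean change is 2 × (24 - k) / 24. Each such patient lowers the mean by 2 / 24 = 0.083 points. The SD is either held at 3, or allowed to grow because responders and non-responders are mixed: √(9 + 4f(1 - f)), with f = k / 24.

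| k | Mean change (%) | Power, SD held at 3 | Mixture SD | Power, mixture SD |
|---|---|---|---|---|
| 0 | 2.00 | 87.8% | 3.00 | 87.8% |
| 1 | 1.92 | 85.0% | 3.03 | 84.4% |
| 2 | 1.83 | 81.8% | 3.05 | 80.5% |
| 3 | 1.75 | 78.1% | 3.07 | 76.2% |

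These rows assume no response at all. A partial response would cost less.

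*Step 3: compare with excluding them.* If two such patients were excluded and not replaced, 22 pairs would give 84.6%. If they were replaced, power would stay at 87.8%.

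**The case against.** Several stronger conclusions might be drawn from these omissions. The documents do not support them.

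- *That these patients cannot show the tested effect.* This follows from the stated mechanism only for a pituitary with no function. Known pituitary disease, past surgery or irradiation may leave partial function and a partial response. For pregnant women, nothing in the documents suggests non-response.
- *That pregnancy would bias the main results.* Pregnancy plainly changes weight and waist, but the primary outcome is hepatic lipid and the secondary is VAT mass. The documents show no effect of pregnancy on either, so the pregnancy point rests on exposure.
- *That the trial is materially underpowered as a result.* The documents give no frequency, and zero is a plausible count. With two complete non-responders, power is still about 80%. Patients with zero effect also pull the result towards no effect, so they cannot create a false positive.
- *That patients have no safety monitoring.* They do: liver tests, glucose and an examination at each visit. What is missing is any check for these two conditions.

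Three further objections deserve weight. The consent pages are not available and may mention pregnancy, but that would not make it one of the criteria that screening applies. The documents state no hazard of this drug in pregnancy and do not discuss cranial irradiation. The pregnancy exclusion is therefore a general safeguard, and the irradiation item extends the plan's own mechanism argument. Finally, GH and IGF-1 are measured, so a failure to respond could be seen afterwards, but no analysis rule uses it.

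**Conclusion.** The point holds in limited form. The main part is safety: followed as written, the plan could enrol a pregnant woman into a year of study drug and invasive testing without any step that would detect it. This rests on the text alone and needs no assumption about numbers.

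The pituitary part is secondary. Patients with known pituitary or hypothalamic disease are eligible and may not test the hypothesis, given the mechanism the plan states. The cost depends on an assumed count: none at 0 of 24, about 3 percentage points of power at 1 (87.8% to 84-85%), and about 6 to 7 at 2 (to 80-82%). Power falls below 80% only from about 3 complete non-responders, and the documents give no reason to expect that many. The case for this exclusion is a cleaner test of the GH hypothesis; the power gain is a lesser benefit.

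**What to change.** Amend the exclusion list under STUDY DESIGN in two ways.

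1. Add pregnancy, confirmed by a pregnancy test in women of child-bearing potential at the baseline visit, before the first dose. That visit is already planned and already includes a blood draw. If the test is also meant to cover the baseline FSIGT and biopsy, its result is needed before them. A test at screening could mean an extra visit for some women, because Study procedures makes the in-person screening visit conditional.
2. Add known pituitary or hypothalamic disease, pituitary surgery or cranial irradiation, checked in the record review that Study procedures already describes.

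The protocol should also say how a pregnancy that arises during the year is handled. The content of that rule is for the investigators to state.

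The cost is amendment wording, one inexpensive test per eligible woman, two more items in the chart review, and possibly a few candidates lost. Dose, visit schedule and analysis do not change.

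### If the 12-month change is the endpoint, the planned tests ignore the 6-month scan of any patient without a 12-month scan, and the plan has no missing-data rule or dropout allowance

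*Combined protocol and SAP*

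**What the plan says.** Under Study Design the trial is single-arm and open-label, with one year of daily self-injection, and "At the baseline, 6 month and 1 year visits subjects will also undergo body composition testing by total body MRI/MRS". Study Procedures repeats this schedule, so each patient should have three scans.

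Statistical Procedures ranks the outcomes. Liver fat comes first: "The primary outcome to be examined will be change in hepatic lipid content". Visceral fat follows in second place: "the secondary outcome will be change in VAT mass with tesamorelin therapy". Neither statement names a time point. The test is given as: "The general analytic approach will be to compare baseline to post-therapy parameters in each subject by paired t-test". The section adds: "Repeated measures ANOVA will test adipose tissue mass change over time". That sentence covers VAT but not hepatic lipid. Only the blood markers have a named end: "For analysis of the blood samples differences between baseline and final study visit for each marker will be compared by paired t-test". Log transformation or nonparametric methods are allowed for non-normal data.

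The sample size is 24 pairs, with 88% power for a hepatic lipid change of 2% with SD 3%, two-sided 5%. The section has no analysis set, missing-data rule, dropout allowance or sensitivity analysis.

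**The concern.** A paired t-test uses a patient only if both values exist. Repeated-measures ANOVA in its classical form drops a patient who lacks any scan. With the 12-month change as the endpoint, someone scanned at baseline and 6 months but not at 12 months is lost from both analyses, although half a year of response has been measured.

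Two things are at stake. First, precision: the power statement counts complete pairs, and a year of treatment with repeated scans and biopsies makes some loss likely. Second, bias: if leaving is related to response, those who stay are a selected group. With one arm, there is no control group in which similar loss could partly offset this. The estimate and the error rate of the primary test could then both be wrong, and the plan has no means of showing it.

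**Working it through.** **1. The plan's own figure.** Inputs from Statistical Procedures: change 2, SD 3, two-sided 5%, n pairs. Power is the probability that a noncentral t with n-1 df and noncentrality (2/3)√n exceeds the critical value in absolute size. For n = 24 the noncentrality is 0.667 × 4.899 = 3.27, the critical value is 2.069, and power is 87.8%. The stated 88% reproduces.

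**2. Power when pairs are lost.** Same formula:

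| Complete pairs | Power |
|---|---|
| 24 | 87.8% |
| 21 | 82.8% |
| 20 | 80.7% |
| 19 | 78.5% |
| 18 | 76.0% |
| 16 | 70.3% |

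Power falls below 80% once 5 of 24 are lost. With random 25% loss, simulation gave about 75% to 77% for the paired t-test and 77% to 82% for a likelihood estimate that uses the 6-month scan.

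**3. Bias of the completer mean.** The documents give no dropout rate, no reasons for leaving and no correlation between the 6- and 12-month changes. Assumptions: true 12-month change -2.0, SD of change 3 at both visits, correlation ρ from 0.6 to 0.8, normal data. A fraction q of below-average 6-month responders leaves after the 6-month scan and nobody else does, so overall loss is q/2.

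Among those who stay, the mean standardised 6-month change moves by q × 0.399 / (1 - q/2), where 0.399 is the standard normal density at zero. The 12-month mean moves by 3ρ times that.

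- 10% loss (q = 0.2): 0.2 × 0.399 / 0.9 = 0.0887. Times 1.8 to 2.4 gives a shift of 0.16 to 0.21, so the completer mean is -2.16 to -2.21.
- 25% loss (q = 0.5): 0.5 × 0.399 / 0.75 = 0.266. Times 1.8 to 2.4 gives 0.48 to 0.64, so the mean is -2.48 to -2.64.
- If only above-average responders leave, the shift changes sign: -1.84 to -1.79 at 10% and -1.52 to -1.36 at 25%.
- If loss is unrelated to response, the shift is zero.

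These patterns are sharp. With graded loss (log-odds of leaving 0.5 to 1 per SD of 6-month change, correlation 0.5 to 0.7) and 20% loss, the completer mean is -2.14 to -2.36 if poor responders leave more, and -1.85 to -1.63 if good responders do.

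**4. Type I error.** With no true effect and loss confined to below-average responders, the same shifts apply around zero. At 25% loss and ρ = 0.8, the SD among stayers is 3√(1 - 0.64 × 0.266²) = 2.93. The noncentrality is 0.638 × √18 / 2.93 = 0.92 and the rejection rate is about 14%; at ρ = 0.6 it is about 10%. At 10% loss it is about 6%. Simulated values move by a few points with how the loss is generated, so the range is about 6% to 16%.

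**5. What a likelihood estimate does.** An estimate that uses the 6-month scan returned -2.0 (or 0 under no effect) in every case in which loss depended only on the 6-month value. When loss at 25% depended on the unseen 12-month change, it gave -2.3 to -2.5 against a true -2.0, so it was biased too.

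**The case against.** A reader might infer that the plan drops everyone who leaves after the 6-month scan and that its result is therefore biased towards those who did well. The documents do not support this.

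- A paired t-test needs baseline and one later scan, not all three. Because post-therapy is undefined, a patient with only a 6-month scan would be kept if the 6-month or last available scan were used. This stands, but it leaves the choice of scan open until the data are seen. The last available scan is no neutral escape: under the graded patterns at 20% loss it gave -1.93 to -1.79 if poor responders leave more and -2.07 to -2.20 if good responders do.
- The ANOVA is planned for adipose tissue mass, so that part concerns VAT and not the primary outcome. No implementation is specified, and the loss of patients with a missing scan applies to the classical form.
- Nothing in the documents says that poor responders leave. Patients cannot feel their liver fat, and no text says they are told scan results. The direction of any bias is open and it may be nil.
- The 25% scenario is severe: half of all below-average responders leave and nobody else does.
- A mixed model is not a cure. It is unbiased only if loss depends on observed values, and it learns little from patients lost before month 6.

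These points limit the claim. They do not remove the gap: no time point, no missing-data rule, and a stated method that ignores scheduled data if the endpoint is 12 months.

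**Conclusion.** The point holds in conditional form. If the 12-month change is the endpoint, the paired t-test for liver fat, and the paired t-test or classical ANOVA for VAT, give no weight to the 6-month scan of a patient without a 12-month scan.

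The power consequence needs no assumption about why patients leave: 88% is the figure for no loss at all, and 19 pairs give 78.5%.

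The bias is possible, not shown. Under the assumptions above, and between 10% and 25% loss, the completer mean runs from about -2.2 to -2.6 if below-average responders leave and from about -1.8 to -1.4 if good responders leave, against a true -2.0. It is correct if loss is random. A type I error of about 6% to 16% belongs to the first pattern with no true effect. The dropout rates and the correlation are assumed; SD 3 and the change of 2 are the plan's own.

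This should be changed before analysis because a better use of scheduled scans costs almost nothing. It does not show that the trial's result will be wrong.

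**What to change.** In Statistical Procedures:

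1. Name the 12-month change from baseline as the primary contrast for liver fat, and likewise for VAT.
2. Analyse both with a mixed model for repeated measures on all available scans at 0, 6 and 12 months, with unstructured covariance and Kenward-Roger degrees of freedom, in all enrolled patients with a baseline scan. Log-transform if skewed, as the plan already allows.
3. Keep the paired t-test as a complete-case sensitivity analysis.
4. Add one sensitivity analysis in which loss depends on unobserved response, for example by shifting the assumed 12-month values of patients who left over a stated range.
5. State the expected loss and give power for the resulting number of 12-month pairs. If 24 pairs are to be kept, enrolment is 24/(1 - loss), rounded up: 27 at 10%, 30 at 20%, 32 at 25%.

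Cost: new wording, slightly more analysis work, and a less favourable stated power or a larger enrolment. No extra scans are needed. With complete data the 12-month contrast is essentially the paired t-test, so nothing is given up.
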